9. TRIAL CONDUCT

9.1. *Domain-specific Data Collection*

9.1.1. Clinical Data Collection

Patients who are randomized in this domain will have the following data collected:

- Treatment allocation at the time of enrollment
- Successful dispensing of study medication
- Gastrointestinal intolerance
- SAE as defined in Core Protocol

9.2. *Criteria for Discontinuation*

Refer to Core Protocol for discontinuation criteria for the participation in UPMC REMAP.

9.3. *Blinding*

9.3.1. Blinding

We will attempt blinding in the following ways. All medication tablets will be void of dosage amounts or stamps that identify dose. Each patient will have the number of pills appropriate to the dose to which they are randomized. For placebo patients, we will randomly select whether they receive 1, 2, or 3 tablets, all of which will be placebo. Placebo pills will appear identical to study drug in color, size, shape, and markings, to the extent legally possible.

9.3.2. Unblinding

N/A

11. ETHICAL CONSIDERATIONS

11.1. *Data Safety and Monitoring Board*

The DSMB should be aware that the superiority, inferiority, or equivalence of different interventions with respect to the primary endpoint is possible, and if equivalence is demonstrated, the optimal treatment may be based on secondary endpoints.

11.2. *Potential Domain-specific Adverse Events*

The drug used in this domain has a known toxicity profile and adverse events are rare.

Domain-specific harms related to metformin include:

- Gastrointestinal intolerance
- Hypersensitivity
- Lactic acidosis
- Hemolytic anemia
- Malabsorption

11.3. *Domain-specific Consent Issues*

Metformin is approved and is in common use in many countries.

The use of prolonged courses of metformin is widely used for diabetes and the doses proposed in this trial are well within the standard range. Clinics will be able to opt out of this domain for all patients at that site if they believe that this intervention is not part of reasonable care of patients

evaluated for elective surgery. Additionally, clinicians may choose not to enroll individual patients if they feel that participation is not the patient's best interests.

12. GOVERNANCE ISSUES

12.1. *Funding of Domain*

The SPRY trial is funded by UPMC.

12.2. *Domain-specific Declarations of Interest*

All investigators involved in UPMC REMAP will maintain a registry of interests with UPMC. These are updated periodically and publicly accessible on the study website.

## **1. UPMC REMAP–SPRY -METFORMIN DOMAIN SAP VERSION**

The version is in this document's header and on the cover page.

### **1.1. Version history**

Version 1: Finalized on 06 September 2023.

### **3. INTRODUCTION**

The population is aging. Over 50 million Americans are greater than 65 years of age. Associated with, but independent of aging, the cumulative effects of medical, social, and environmental stressors lead to frailty. The physiologic stress associated with the surgical treatment of disease is an age and frailty accelerating physiologic stressor, progressing frailty and further depleting resilience. As such, aging and frail patients, whom undergo over one third of all surgical interventions, have an increased risk of postoperative morbidity and mortality for all levels of physiologic surgical stress.

Strategies to Promote ResiliencY (SPRY) aimed to use the age and frailty inducing surgical intervention as an efficient experimental model to stabilize or even reduce frailty and the associated adverse postoperative outcomes. Using a randomized, embedded, multifactorial, adaptative platform (REMAP) trial strategy, we hypothesized that the pleiotropic and anti-inflammatory properties of metformin administered to non-diabetic patients in the perioperative period would reduce the age-accelerating physiologic stress as demonstrated through an increase in postoperative 90-day hospital free days (HFD) following an elective, major surgical intervention.

### **4. DESIGN CONSIDERATIONS**

SPRY investigates the effects of perioperative metformin on the primary outcome of 90-day HFD by pragmatically randomizing patients with different preoperative exposure durations to placebo or one of three doses of metformin. We planned to evaluate three preoperative exposure durations (short, 7-28 days; intermediate, 29-90 days; and long, 90 days) as well as three doses of metformin extended release (ER; 500mg, 1000mg, and 1500mg) among patients undergoing 14 surgical types (i.e., surgical strata). The primary Bayesian model, prespecified prior to patient enrollment, is a Bayesian ordinal logistic regression to estimate the effect of dose and duration of metformin on the distribution of HFD under placebo adjusting for expected differences given the surgical type/strata. Due to early discontinuation of the trial, 14 planned surgical types were consolidated into 6 surgical categories and three perioperative exposure durations were consolidated into one category for the primary Bayesian model.

In response to the COVID-19 pandemic, SPRY temporarily closed enrollment on 3/20/2020. On 8/17/2020, SPRY continued to enroll through in-person clinic-based screening and enrollment but

expanded to also complete virtual patient screening and enrollment. As a result, two enrollment strategies were utilized – in-person and virtual enrollment.

Prespecified adaptive randomization strategies for dose and duration dropping as well as thresholds for treatment efficacy, inferiority, futility, and equivalence were defined for interval analysis with 500 patients enrolled and for every additional 500 patients up to 2,500 followed for 90 days. The complete description of the *a priori* statistical analysis plan was completed prior to patient enrollment and previously published. However, the trial was discontinued prior to the first interval analysis due to low enrollment in the setting of COVID-19 and poor tolerance of perioperative study drug. As such, no interim results triggered response adaptive randomization. As previously planned, trial termination would result in public disclosure and a declaration of results.

## **5. UNBLINDING**

The original intent was for the timing of unblinding to be determined by completion of predetermined endpoints by all subjects enrolled. Unblinding at the time of completion of secondary endpoints was not considered due to the possibility of their occurrence very early in the trial. As SPRY has closed prior to enrolling the goal number of subjects, unblinding will not occur until the statistical analysis plan described in this document is finalized.

## **6. INTERVENTIONS**

There is one active intervention and one control within this analysis plan:

- 1- Metformin
- 2- Placebo

Preoperative duration of study drug was pragmatically chosen based upon the time interval between the time of enrollment and scheduled operating room date including:

- 1- Short – 7-28 days
- 2- Medium – 29-90 days
- 3- Long – >90 days

Preoperative duration is not considered in the primary model but was considered in planned sensitivity analyses. Patients were randomly assigned,  $\sqrt{3}$ :1:1:1 to placebo and the 3 doses of metformin:

- 1- Placebo
- 2- Metformin 500mg ER
- 3- Metformin 1000mg ER
- 4- Metformin 1500mg ER

The dosing of and route of administration of metformin guidance included to take an oral dose once daily and complete all dispensed medication from the provided pill bottle.

## **7. DISEASE STATES**

The disease state under investigation includes the older (age  $\geq 60$ ) and/or medically frail (age  $<60$  with  $>2$  Charlson Comorbidity Index) non-diabetic patients undergoing a major surgical intervention. Major surgical interventions analyzed include 6 surgical strata:

- 1- Colon and Rectal Surgery, enrolling from the following clinics
  - a. Colon and Rectal Surgery at UPMC Presbyterian University Hospital
  - b. Center for Perioperative Care at UPMC Presbyterian Hospital
  - c. Center for Perioperative Care at UPMC Shadyside Hospital
  - d. Pitt+Me
- 2- General and Oncological Surgery, enrolling from the following clinics
  - a. General Surgery at UPMC Presbyterian University Hospital
  - b. General Surgery at UPMC Saint Margaret's Hospital
  - c. Surgical Oncology at UPMC Presbyterian University Hospital, at Presbyterian
  - d. Surgical Oncology at UPMC Presbyterian University Hospital, at Shadyside
  - e. General Surgery at UPMC Passavant Hospital
  - f. Center for Perioperative Care at UPMC Presbyterian Hospital
  - g. Center for Perioperative Care at UPMC Shadyside Hospital
  - h. Pitt+Me
- 3- Orthopedic/Spine Surgery, enrolling from the following clinics
  - a. Ortho/Spine Surgery at UPMC Presbyterian University Hospital
  - b. Center for Perioperative Care at UPMC Presbyterian Hospital
  - c. Center for Perioperative Care at UPMC Shadyside Hospital
  - d. Pitt+Me

- 4- Neurosurgery, enrolling from the following clinics
  - a. Center for Perioperative Care at UPMC Presbyterian Hospital
  - b. Center for Perioperative Care at UPMC Shadyside Hospital
  - c. Pitt+Me
- 5- Vascular Surgery, enrolling from the following clinics
  - a. UPMC East Hospital
  - b. UPMC Mercy Hospital
  - c. UPMC Saint Margaret's Hospital
  - d. Center for Perioperative Care at UPMC Presbyterian Hospital
  - e. Center for Perioperative Care at UPMC Shadyside Hospital
  - f. Pitt+Me
- 6- Other, enrolling from the following clinics
  - a. Center for Perioperative Care at UPMC Presbyterian Hospital
  - b. Center for Perioperative Care at UPMC Shadyside Hospital
  - c. Pitt+Me (on-line recruitment)

## **8. ANALYSIS POPULATIONS**

All participants who were randomized and underwent a surgical intervention within 365 days of randomization will be considered in our analysis population.

- SPRY intention to treat (ITT): This population consists of all patients enrolled and randomized to any treatment dose and duration. This population will only include those who underwent a surgical intervention at any time in the 365 days following randomization. All comparisons will be made based up the randomization table allocated treatment.
- SPRY per protocol analysis (PPA): This population consists of all patients enrolled and randomized who also completed randomization table allocated treatment and underwent a surgical intervention within 365 days of enrollment. Adherence to the protocol is determined by those who confirmed compliance with study drug at their 90-day postoperative evaluation with the study team. Compliance is defined by the verbal confirmation of study drug completion at the 90-day follow up timepoint.

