Outcome measures	
Primary REMAP endpoint: hospital free days at day 90 after the surgical encounter
 
Secondary REMAP endpoints refer to Core Protocol
 
Secondary domain endpoints:
 
 1. Gastrointestinal distress causing discontinuation of the medication 2. Lactic acidosis 3. Hepatic dysfunction 
Serious Adverse Events (SAE) as defined in CORE protocol

TABLE OF CONTENTS

1. ABBREVIATIONS	6
2. PROTOCOL APPENDIX STRUCTURE	7
3. Metformin DOMAIN-SPECIFIC APPENDIX VERSION	7
3.1. Version History.....	7
4. Metformin DOMAIN GOVERNANCE.....	8
4.1. Domain Members	8
4.2. Contact Details.....	10
5. Metformin DOMAIN-SPECIFIC WORKING GROUP AUTHORIZATION	11
6. BACKGROUND AND RATIONALE	11
6.1. Domain Definition	11
6.2. Domain-specific Background	11
6.2.1. Guideline Recommended Use of Metformin and Potential Applications	12
6.2.2. Metformin Mechanisms of Action.....	13
6.2.3. Association of Metformin with Longevity in Small Clinical Trials	13
6.2.4. Metformin Safety Profile	13
7. DOMAIN OBJECTIVES	14
8. TRIAL DESIGN	15
8.1. Population.....	15
8.2. Eligibility Criteria	15
8.2.1. Inclusion Criteria for this Domain	15
8.2.2. Exclusion Criteria from this Domain	15
8.3. Interventions	16
8.3.1. Research Testing	16
8.3.2. Study Drug Intervention.....	16
8.3.3. Timing of Initiation of Intervention.....	17
8.3.4. Duration of Administration of Study Drug	17
8.3.5. Temporary Suspension of Study Drug.....	17
8.3.6. Suspension of Study Drug at the Direction of the Treating Clinician.....	17
8.3.7. Collection of Blood Samples	18
8.3.8. Collection of Samples for Microbiome Sub-study	18
8.3.9. Collection of questionnaires	19

8.3.10. Muscle Biopsy Sub-Study	21
8.4. Endpoints	23
8.4.1. Primary Endpoint	23
8.4.2. Secondary Endpoints.....	23
9. TRIAL CONDUCT	24
9.1. Domain-specific Data Collection	24
9.1.1. Clinical Data Collection	24
9.2. Criteria for Discontinuation	24
9.3. Blinding	24
9.3.1. Blinding	24
9.3.2. Unblinding.....	24
10. STATISTICAL CONSIDERATIONS.....	24
10.1. Domain-specific Stopping Rules.....	24
10.2. Strata.....	25
10.3. Timing of Revealing of Randomization Status	25
10.4. Interactions with Interventions in Other Domains	25
10.5. Post-trial Sub-groups.....	26
11. ETHICAL CONSIDERATIONS	26
11.1. Data Safety and Monitoring Board	26
11.2. Potential Domain-specific Adverse Events	26
11.3. Domain-specific Consent Issues.....	26
12. GOVERNANCE ISSUES	27
12.1. Funding of Domain.....	27

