8.3.3. Timing of Initiation of Intervention

The intervention is to begin on the day following the evaluation of the eligible and consented subject at the pre-operative clinic/surgeon's office. Daily oral doses will continue through the hospital admission for elective surgery. For patients without side effects, dosing will continue daily for 90 days after the surgical encounter.

Patients will be contacted between the pre-operative clinic/surgeon's office visit and surgery to evaluate study drug compliance as well as any adverse events associated with the study drug.

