## 9. ENDPOINTS

The following endpoints will be analyzed, displayed graphically, and summarized through descriptive statistics. Endpoints will be reported among the analysis populations as well as among the pre-specified subgroups. Categorical endpoints may be collapsed where appropriate in case of data sparseness.

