### 9.2. Secondary Endpoints

Secondary domain-specific outcome measures include information about EHR based alerts reported during the index elective surgical admission, perioperative outcomes, and surgical outcomes.

Specifically, they include:

- Perioperative outcomes (enrollment to postoperative 90 days)
  - Gastrointestinal intolerance (dichotomous; present/absent)
  - SAE as defined in Core Protocol (mild, moderate, severe, life threatening/disabling; adjudicated as related, possibly related, unrelated)

- Surgical outcomes
  - Index admission
    - Postoperative intensive care unit (ICU) admission (dichotomous; any admission/none)
    - ICU length of stay (LOS; continuous, days)
    - Hospital LOS (continuous, days)
    - Discharge disposition (categorical; Home, SNF/LTAC, Death/Hospice)
    - In-hospital mortality (dichotomous; yes/no)
  - 30-day outcomes
    - Organ failure free days (i.e., vasopressor exposure, hemodialysis, or mechanical ventilation; continuous, days)
    - Surgical site infection, as defined by NSQIP and the CDC (categorical)
    - Surgical site occurrence, as defined by Ventral Hernia Working Group (categorical)
  - 90-day outcomes
    - Reoperation/reintervention, both incidence and total number (dichotomous, time to event; any/none and continuous, number)
    - Readmission (dichotomous, time to event; any/none, days)
    - Venous thromboembolic events including deep vein thrombosis and pulmonary embolus after surgery (dichotomous, time to event; any/none, days)
    - Mortality (dichotomous, time to event; yes/no, days)

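### Gastrointestinal intolerance is counted from enrolment but modelled only in patients who reach surgery, so the modelled comparison leaves out intolerance in the other randomised patients

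*SAP*

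**What the plan says.** **Endpoint.** SAP 9.2 lists GI intolerance as a present/absent outcome, with a window from enrolment to postoperative day 90.

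**Exposure.** Protocol 8.3.3 says: "The intervention is to begin on the day following the evaluation of the eligible and consented subject". SAP 6 allows pre-operative exposure of more than 90 days.

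**Analysis sets.** SAP 8 first describes the ITT set as everyone enrolled and randomised, then narrows it: "This population will only include those who underwent a surgical intervention at any time in the 365 days following randomization". The per-protocol set (PPA) also requires surgery within 365 days, plus completed treatment: "Compliance is defined by the verbal confirmation of study drug completion at the 90-day follow up timepoint".

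**Where the endpoint is analysed.** SAP 13.2 fits the secondary-endpoint regressions in the ITT and PPA sets. SAP 9 says: "Endpoints will be reported among the analysis populations as well as among the pre-specified subgroups". SAP 11 also plans summaries of baseline and perioperative information for all randomised participants. SAP 13.2.1 adds counts and percentages for dichotomous, categorical and time-to-event endpoints, referring back to Section 11.

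**Non-operated patients elsewhere.** SAP 13.3 runs the subgroup models of 90-day hospital-free days (HFD-90) in the ITT and PPA sets. Its surgical-strata list includes a no-operation level, which is exempt from merging when small.

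**The concern.** SAP 4 gives poor tolerance of study drug as one of two reasons for discontinuing the trial, so readers will look for the metformin-placebo comparison of intolerance. As planned, the model for that comparison is conditional on having surgery, an event that follows both randomisation and the start of drug. For HFD-90 the restriction is natural, because its clock starts at surgery. For an endpoint whose clock starts at enrolment, it removes people who were already at risk and may already have had the event.

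The PPA selects further. Protocol 8.3.3 says: "For patients without side effects, dosing will continue daily for 90 days after the surgical encounter". A set defined by drug completion is therefore partly selected on tolerance itself.

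The ITT label adds to the difficulty, since a reader will take it to mean everyone randomised.

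**Working it through.** The documents give no intolerance rate for this trial, no proportion not operated on and no figure for the link between the two. There is no planned figure to reproduce, and what follows is illustration.

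**1. Who is left out.** Take a patient who is randomised, starts drug, develops GI intolerance and has no surgery within 365 days.
- SAP 9.2: the event falls after the start of the window.
- SAP 8: the patient is in neither the ITT set nor the PPA.
- SAP 13.2: the patient is therefore in no model.

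**2. Effect on the odds ratio.** Let p be the true intolerance rate in an arm, and s1 and s0 the probabilities of surgery with and without intolerance. Among operated patients the odds of intolerance are p·s1 / [(1 − p)·s0], which is the true odds times s1/s0. Hence, with M for metformin and P for placebo,

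OR(operated) = OR(true) × (sM1/sM0) / (sP1/sP0).

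The multiplier does not depend on the intolerance rates. Assume s0 = 0.95 in both arms (5% non-operation).

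| Non-operation with intolerance | Multiplier |
|---|---|
| Same in both arms | 1.00 |
| 15% in one arm, no link in the other | 0.85/0.95 = 0.89 if metformin; 1.12 if placebo |
| 25% in one arm, no link in the other | 0.75/0.95 = 0.79 if metformin; 1.27 if placebo |
| 25% in one arm, 15% in the other | 0.75/0.85 = 0.88 if metformin has 25%; 1.13 if placebo has 25% |

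**3. Effect on absolute rates.** Rate among operated = p·s1 / [p·s1 + (1 − p)·0.95]. The 30% and 60% values are the ends of the range that Protocol 6.2.3 reports for other metformin regimens; 20% is assumed.

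| True rate | s1 = 0.85 | s1 = 0.75 |
|---|---|---|
| 20% | 18.3% | 16.5% |
| 30% | 27.7% | 25.3% |
| 60% | 57.3% | 54.2% |

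Absolute rates fall even when the link is the same in both arms.

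**4. Share of events outside the model.** Let m be the all-randomised rate, u the proportion not operated on, and k the relative risk of no surgery with versus without intolerance. Then q = u/(mk + 1 − m), the share of events left out is kq, and the operated-only rate is m(1 − kq)/(1 − u). For m of 30% to 60%, u of 5% to 20% and k of 1 to 3 (u and k assumed), the share left out runs from 5% to 37.5%.
- With k = 1 events are lost but the rate is unchanged.
- With m = 0.30, u = 0.20 and k = 3: q = 0.20/1.6 = 0.125, the share left out is 37.5%, and the 30% rate appears as 0.30 × 0.625/0.80 = 23.4%.

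**5. The PPA on its own.** Suppose 50% of patients with intolerance and 10% of those without stop drug (assumed). True rates of 20%, 30% and 60% then appear as 12.2%, 19.2% and 45.5%. For 30%, the sum is 0.15/(0.15 + 0.63).

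**6. The no-operation level.** SAP 13.3 puts it in HFD-90 models run in the ITT and PPA sets. SAP 8 excludes non-operated patients from both. SAP 9.1 starts HFD-90 at the date of surgery, so these patients have no index date. The level has no eligible members and no defined outcome.

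**The case against.** **Descriptive reporting.** A reader might infer that intolerance in non-operated patients goes unreported. The documents do not support that. SAP 9.2 classes GI intolerance as a perioperative outcome, SAP 11 summarises perioperative information for all randomised participants, and SAP 13.2.1 points to Section 11. SAP 9 also allows reporting within pre-specified subgroups, one of which is no operation. An all-randomised table is plausible but not assured, since SAP 11 never names GI intolerance and also says that analyses are done in the ITT and PPA sets. The point is confined to the modelled comparison.

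**Serious adverse events.** It is also tempting to say that graded serious adverse events have no reporting plan beyond SAP 11. SAP 13.2.1 covers categorical endpoints with counts and percentages.

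**No bias is shown.** This stands. Nothing in the documents links GI intolerance to cancelled surgery, and Protocol 6.2.3 describes the symptoms as self-limited. A difference between arms is conceivable: on placebo, GI symptoms in colorectal or oncological patients may come from the surgical disease. That is only a possibility.

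**The PPA has no events.** The protocol summary words the endpoint as "Gastrointestinal distress causing discontinuation of the medication", from which a reader might infer that the PPA can contain no events. The SAP's endpoint is present/absent, so a patient with transient symptoms who completed drug still counts.

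**The window is defined by surgery.** Protocol 8.4.2 ties these outcomes to the index procedure, the SAP window closes at postoperative day 90, and the scheduled compliance check in SAP 12 is at that visit. This is a fair reason to show the wider comparison beside the operated-only model rather than in its place. It does not justify leaving the wider comparison out, because the SAP opens the window at enrolment.

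**Conclusion.** The gap is clear from the text: the model of an endpoint counted from enrolment is restricted to patients who later have surgery. Whether this distorts the result cannot be determined from the documents. Absolute rates are biased if intolerance is linked to non-operation, and the odds ratio only if that link differs between arms. Neither condition is shown. Under the assumed inputs the odds-ratio multiplier lies between 0.79 and 1.27, and is 1.00 when the link is equal.

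The PPA cannot support conclusions about tolerance, because membership depends on completing the drug.

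The harm comparison is a cheap improvement. The no-operation level for HFD-90 is wrong as written.

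**What to change.** - Add a GI-intolerance comparison, with serious adverse event counts, in all randomised patients (or all dispensed study drug, which Protocol 9.1.1 records), by allocated arm from enrolment.
- State the end of the window: postoperative day 90 if operated on within 365 days; otherwise death, last contact or day 365 after randomisation, whichever comes first. Report follow-up time by arm.
- Show this comparison beside the operated-only model.
- Draw no tolerance conclusions from the PPA.
- Tabulate non-operation by arm, with reasons where recorded.
- Label the operated set modified ITT.
- Remove the no-operation level from the HFD-90 subgroup models and report those patients descriptively.

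**Cost.** SAP wording, one further comparison and one table. Some data sources already exist: Protocol 8.3.3 plans contact about compliance and adverse events before surgery, and SAP 12 records reported early stopping. The downside is that harm ascertainment may be less complete in patients never operated on, so some chart review may be needed and the limitation should be stated. If unblinding has already taken place, the added comparison should be labelled exploratory under SAP 13.4.

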8.3.4. Duration of Administration of Study Drug

The duration of Metformin therapy is a complimentary research question in this domain. In the short course intervention, subjects will receive the study drug (metformin or placebo) within 7-28 days prior to the elective surgical encounter. In the intermediate course therapy, subjects will receive the study drug for 29-90 days prior to surgery. In the long course therapy, patients receive a longer course of study drug prior to surgery when the pre-operative evaluation occurs far enough in advance (e.g., >3 month). All patients will receive study drug for 90 days after the surgical encounter.

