### 9.1. Primary Endpoint

The primary endpoint for this domain is the REMAP primary outcome of hospital free days at 90 days after the index date (HFD-90). The index date for HFD-90 outcome is defined as the date of the elective surgical encounter.

Hospital free days Score	Score
-1	Patient died during surgery or within the 90 days following their surgical intervention
0	No days out of the hospital in the 90 days following the surgical intervention
1-90	One to 90 days out of the hospital and alive in the 90 days following the surgical intervention

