## 12. TREATMENT DELIVERY

Following randomization, study drug was either provided to the subjects in clinic or study drug was mailed directly to their home. Study drug compliance was monitored at the postoperative 90-day interaction with the study team. At this time, participants who discontinued their medications were determined not adherent and those who continued were adherent. In addition, if patients reported early termination or non-adherence to study drug, this was recorded by study coordinators and reported.

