## 13. ANALYTIC APPROACH

Primary inferential analyses will be done using a Bayesian approach. Sensitivity analyses will be conducted using both Bayesian and Frequentist approaches, as described. Secondary endpoints will be analyzed using frequentist approaches. A summary of the analyses methods is provided below. For all frequentist models, statistical significance will be defined as a one-sided p-value of <0.025, and for all Bayesian models a one-sided posterior probability > 0.975. If stable inference cannot be made due to sparseness of data within strata/categories, data may be further collapsed as needed.

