### 13.1. Primary Analysis of Primary Endpoint

#### *Primary Analysis*

The **primary analysis model** is a Bayesian cumulative logistic model for the ordinal primary endpoint. The primary analysis is to be completed in both the ITT and PPA populations described above.

In the primary analysis, observations will be pooled across pre-operative duration of study drug and will borrow across study drug dose. The primary endpoint for this model is HFD-90 and will be compared across the placebo and three levels of study drug dose. The general Bayesian cumulative logistic model is defined below:

Throughout we assume for patient  $i$ ,  $y_i$  is the observed 90-day HFD,  $g(i)$ , is the surgical strata from 1:G,  $d(i)$  is the pre-op duration from 1:3 with 1 = short, 2 = intermediate, and 3=long, and  $t(i)$  is the intervention from 1:4 with 1 = placebo, 2 = 500mg, 3 = 1000mg, and 4 = 1500mg.

The general Bayesian ordinal logistic regression model is used to estimate the effect of dose and duration of metformin on the distribution of HFD-90 under placebo adjusting for expected differences given the surgical strata. The ordinal scale parameterization is a generalized version of the dichotomous parameterization where we model all cumulative probabilities of 90-day HFD being less than or equal to a cutpoint  $c$ , where  $c = -1, \dots, 89$ . Given each cutpoint  $c$ , we denote the 91 dichotomized versions of 90-day HFD for patient  $i$  as  $\gamma_{c,i}$  where  $\gamma_{c,i} = 1$  if 90-day HFD is in  $[-1, c]$  and  $\gamma_{c,i} = 0$  if 90-day HFD is in  $[c+1, 90]$  for  $c = -1, \dots, 89$ .  $\gamma_{c,i}$  is then modeled throughout as:

$$\gamma_{c,i} \sim \text{Bernoulli}(\phi_{c,i});$$

$$\text{logit}(\phi_{c,i}) = \gamma_c + \mu_i;$$

where  $\mu_i$  is a patient-specific mean function and  $\gamma_c$  is common across all patients. To assure model stability, if there is an outcome in the ordinal scale that did not occur in the data, then that outcome will be combined with a neighboring outcome (the worse outcome). For example, if the outcome 11 never occurred, then a combined outcome of 10 & 11 will be modeled for the analysis.

The subject-specific mean function is as follows:

$$\mu_i = \alpha_{g(i)} + \theta_{t(i), d(i)}.$$

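### The per-protocol set removes 90-day deaths by rule, yet the primary and mortality models run in it with no stated ranking against ITT

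*SAP*

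**What the plan says.** SAP section 8 defines the PPA as randomized patients "who also completed randomization table allocated treatment and underwent a surgical intervention within 365 days of enrollment". It then fixes how completion is established: "Compliance is defined by the verbal confirmation of study drug completion at the 90-day follow up timepoint". SAP section 12 agrees on the timing: "Study drug compliance was monitored at the postoperative 90-day interaction with the study team". Protocol section 8.3.4 sets the length of treatment: "All patients will receive study drug for 90 days after the surgical encounter". Protocol section 8.3.9 places the 90-day contact at day 90 with a window of plus 28 days, so it does not open before day 90.

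SAP section 9.1 gives the score -1, the worst level of HFD-90, to this event: "Patient died during surgery or within the 90 days following their surgical intervention". On populations, section 13.1 states: "The primary analysis is to be completed in both the ITT and PPA populations described above". Section 13 sets a single criterion, "for all Bayesian models a one-sided posterior probability > 0.975". Section 13.2 runs the secondary endpoints in both populations, and section 9.2 lists in-hospital mortality and 90-day mortality among them.

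**The concern.** Membership of the PPA depends in part on the outcome being analysed. A patient who dies within 90 days of surgery fails both entry conditions, because the course is unfinished and nobody is there to confirm it. Neither document offers a proxy report, a rule for adherence up to death, or an exception for deaths.

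The PPA comparison of HFD-90 is therefore conditional on survival to the day-90 contact, and a mortality effect in either direction cannot show in it. The PPA 90-day mortality models have no events in either arm. Printed without explanation, zero deaths per arm could be read as a safety result when it follows from the definition. Because the SAP does not call the PPA supportive, its text leaves a survival-conditioned result level with the ITT result.

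Two related matters are not part of this point: selective loss through drug intolerance, and the death versus no-death report in the frequentist sensitivity section, which is descriptive.

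**Working it through.** **1. The rule against the outcome.**

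| Requirement or outcome | Source | Patient who dies before the day-90 contact |
|---|---|---|
| Completed allocated treatment, which runs 90 days after surgery | SAP 8; Protocol 8.3.4 | Not met |
| Verbal confirmation at a contact no earlier than day 90 | SAP 8 and 12; Protocol 8.3.9 | Not met |
| HFD-90 score | SAP 9.1 | -1 |

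One exception is possible: a patient who confirms completion on day 90 and dies later that day. It is negligible. Survivors who are not reached are also excluded. In-hospital mortality is empty in the same way, except for a death after a confirmed contact during an index stay longer than 90 days.

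**2. Do other provisions restore these patients?** No.
- Collapsing sparse categories (SAP 9 and 13) acts on patients already in the set.
- SAP 11 ties modelling to event frequency, but its explicit no-model trigger is fewer than 10 subjects.
- The imputation rule (SAP 13.5) covers data not captured. A death is captured, in a patient outside the PPA.
- The SAP 13.1 rule for unobserved outcomes merges them with the worse neighbour. The level -1 has none.

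**3. The mortality models.** With no events, for example 0/73 versus 0/127 (N = 200 at the allocation ratio), the logistic intercept runs to -25.6 with SE 25,281 and the treatment coefficient has SE 31,725, so there is no finite estimate. The Cox partial likelihood has no terms.

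**4. Expected deaths removed.** The documents give no death rate and no final sample size, so both are assumed. The trial stopped before the first interval analysis at 500 patients (SAP 4), so N = 200, 300 and 499 are used. Allocation is √3:1:1:1 (SAP 6), giving a placebo share of √3/(√3 + 3) = 0.366 and a metformin share of 0.634. Expected deaths = N × (0.366 p₀ + 0.634 p₁), with placebo mortality p₀ of 1%, 2% or 5% and metformin mortality p₁ double or half of it.
- N = 200: 1.4 to 16.3
- N = 300: 2.0 to 24.5
- N = 499: 3.4 to 40.8

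For example, N = 300 with 2% versus 4%: 300 × 0.366 × 0.02 + 300 × 0.634 × 0.04 = 2.2 + 7.6 = 9.8.

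**5. Effect on the HFD-90 odds ratio.** A proportional odds model was fitted by maximum likelihood to expected cell proportions, pooled metformin versus placebo. Survivors' hospital days were identical in both arms: negative binomial, size 0.9, mean 2, 4 or 8 days (assumed), in 19 ordered groups plus death. Odds ratios are for worse HFD-90; ranges span the three means.

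| Placebo mortality | Doubled by metformin, deaths kept | Halved, deaths kept | PPA as written |
|---|---|---|---|
| 1% | 1.03 | 0.98–0.99 | 1.00 |
| 2% | 1.06–1.07 | 0.97 | 1.00 |
| 5% | 1.16–1.17 | 0.92–0.93 | 1.00 |

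**6. Against sampling error.** The largest shift is ln(1.168) = 0.155. The lower bound on the standard error is √(3/(n × 0.366 × 0.634)):

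| N | All retained | 75% in PPA | 50% in PPA |
|---|---|---|---|
| 200 | 0.254 | 0.294 | 0.360 |
| 300 | 0.208 | 0.240 | 0.294 |
| 499 | 0.161 | 0.186 | 0.228 |

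The retention shares are assumed. Allowing for ties raises these values by about 3% at most. The shift is at most 0.155/0.186 = 0.83 SE in the PPA (N = 499, 75%) and 0.155/0.360 = 0.43 SE at N = 200 with 50% retained.

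**The case against.** The strongest reply is that this is a labelling matter with little consequence. A completer set is conditional on survival by nature, ITT is intact, and a model with no events visibly yields nothing. SAP 11 could lead the analyst simply to describe a zero-event endpoint, and section 13.2.1 already calls for counts and percentages. Equal standing is inferred from silence: the shared 0.975 threshold also covers sensitivity models, and the Core Protocol and the published original plan, which are not among the documents, may rank the populations.

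The size is also smaller on the contrast that the primary model estimates, each dose against placebo. Without borrowing, the standard error bound is √(3 × (1/n₀ + 1/n₁)), which at N = 499 is 0.212, 0.245 and 0.300 for 100%, 75% and 50% retention. The largest shift is then 0.155/0.245 = 0.63 SE. At 2% versus 4% mortality it is ln(1.065)/0.245 = 0.26 SE. If mortality is equal in the two arms, deaths cause no shift.

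Most of this stands as a limit on size, and 0.83 SE remains valid as an upper bound. It does not answer the main point. Description instead of modelling does not bring the deaths back, and an unexplained zero count can still mislead. The accurate statement on ranking is that this SAP gives none; it labels other analyses as sensitivity analyses but not the PPA. Excluded deaths could be found by subtracting PPA counts from ITT counts, but the number of unreached survivors could not.

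**Conclusion.** The concern holds and should be fixed. Apart from a death on day 90 after a confirmed contact, the PPA excludes all deaths within 90 days of surgery, whatever the true rates. The 90-day mortality comparison there is empty, and the in-hospital one nearly so. The SAP runs its primary analysis in that set without placing it below ITT.

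The exclusion follows from the text and needs no assumption. The effect on the HFD-90 odds ratio does rest on assumptions: mortality of 1% to 5%, doubling or halving by metformin, identical hospital days in survivors, and the sample sizes and retention shown. Within those it is below one standard error. ITT results are unaffected.

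**What to change.** 1. In SAP 13.1, name ITT as the sole population for primary inference and label the PPA supportive.
2. In SAP 9.2 and 13.2, make in-hospital and 90-day mortality comparisons in ITT only.
3. With every PPA result, state that it is conditional on survival to the day-90 contact, and report by arm the deaths and the unreached survivors excluded.

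Items 1 and 2 are wording; item 3 adds one count table. No new data are needed. If unblinding has already taken place, the same clarification can be made openly in the report and dated.

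A supportive version of the PPA that keeps decedents judged adherent until death is optional. It depends on coordinator records made only when patients reported stopping (SAP 12), and it can overweight deaths. At an assumed 2% versus 4% mortality and a mean of 4 hospital days, keeping all decedents but only 75% or 50% of survivors gives an odds ratio of 1.08 or 1.12, against 1.06 in ITT and 1.00 as written.
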